# 9.2 Visit 2 (Day $8 \pm 2$ ): Follow-Up

At this visit, the investigator or designee will:

Observe/query the subject about any changes in his/her health since the previous study visit. Initiate/update the appropriate AE form as required.

- Review the subject's compliance with the study requirements, including twice daily application of test article as directed at Visit 1.
- Query the subject about any changes in concomitant medications/therapies (including the bland emollient and the investigator-approved medicated shampoo as appropriate) since the previous study visit and document the findings.
- Record LSRs associated with topical application of the test article (see Section 10.5).
- Perform photography, at the discretion of the investigator (selected study sites only; see Section 11).
- Perform clinical evaluations (IGA and clinical signs of psoriasis; see Section 10).
- Document the percent BSA with active psoriasis in the Treatment Area. This will include any remaining lesions identified at the Baseline Visit AND any new psoriatic lesions that may be present at this visit.
- Review subject instructions on the proper application of the test article (Appendix 1) as well as review (and discuss any discrepancies or concerns with the subject regarding their use of the diary), collect, and dispense another (new) Subject Diary (Appendix 2) and review completion instructions.
  - o Instruct the subject to continue twice daily application of the test article as instructed to all psoriatic plaques in the Treatment Area.
- Collect and weigh used canisters of test article and weigh/dispense an additional canister of test article if necessary (see Appendix 4).
- Dispense bland emollient, as required.

<sup>13 Two applications of test article should be applied each day (approximately 8 hours or more separation between dose applications). If Visit 1 occurs in the late afternoon or evening, only one application will be possible on Day 1 and the time of this first application should be recorded on the Subject Diary (Appendix 2).

• Re-instruct the subject on the proper application of the test article and bland emollient. If necessary, to enhance compliance and proper application of the test article, the site may supervise test article application at this visit.

• Schedule Visit 3 (Day 15 + 3). Subjects should be instructed not to apply the test article within 4 hours prior to the scheduled final clinic visit.

### 9.3 Visit 3 (Day 15 + 3): Final Visit

These activities may occur as scheduled at the end of the treatment period or earlier if the subject is to be dropped from the study.

At this visit, the investigator or designee will:

- Observe/query the subject about any changes in his/her health since the previous study visit. Initiate/update the appropriate AE form as required.
- Review the subject's compliance with the study requirements.
- Query the subject about any changes in concomitant medications/therapies (including the bland emollient and the investigator-approved medicated shampoo as appropriate) since the previous study visit and document the findings.
- Record LSRs associated with topical application of the test article (see Section 10.5).
- Perform photography (selected study sites only; see Section 11).
- Perform clinical evaluations (IGA, clinical signs of psoriasis, and pruritus; see Section 10).
- Record the location of remaining plaques in the Treatment Area in the CRFs.
- Document the percent BSA with active psoriasis in the Treatment Area. This will include any remaining lesions identified at the Baseline Visit AND any new psoriatic lesions that may be present at this visit.
- Perform a UPT for all WOCBP.
- Collect and weigh all canisters of used/unused test article (see Appendix 4).
- Review the subject's diary for completeness of doses applied and times of application. Ask the subject if they applied the test article prior to the clinic visit.
- Discharge subject from the study.

### 10. CLINICAL EVALUATIONS

The following clinical evaluations will be performed per the schedules noted. The same expert grader should ideally complete the evaluations for a given subject throughout the study. If this is not possible (e.g., scheduling conflict, etc.), a different expert grader with overlapping experience with the subject and the study should complete the evaluations.

At Visit 1, the investigator will record the anatomical locations of the psoriatic plaques to be treated with the test article in the CRFs. The psoriatic plaques to be treated must include a minimum of 2% and no more than 12% BSA (see Section 10.4) excluding the face, scalp, groin, axillae, and other intertriginous areas. At the final visit, the investigator will record

[figure not shown]
the anatomical locations of the remaining psoriatic plaques (excluding the face, scalp, groin, axillae, and other intertriginous areas) in the CRFs.

### 10.1 Investigator's Global Assessment (IGA)

The IGA score is a static evaluation of the overall or "average" degree of severity of a subject's disease, taking into account all of the subject's psoriatic lesions (excluding those on the face, scalp, groin, axillae, and other intertriginous areas) by the investigator or designee as the subject appears on the day of the evaluation. This evaluation takes into consideration the three individual characteristics of psoriasis (scaling, erythema, and plaque elevation) with the IGA score at each visit representing the average degree of scaling, erythema, or plaque elevation that is present amongst all of the lesions eligible for treatment.

The investigator should NOT refer to any other assessments to assist with this evaluation. This evaluation is NOT a comparison with the IGA at any other visit or a mathematical calculation based on the clinical signs of psoriasis scores. The Visit 1 assessment must be made PRIOR to the first application of the test article and subsequent assessments should be made four hours or more after any application of the test article. At every study visit, evaluate all active psoriasis plaques (excluding those on the face, scalp, groin, axillae and other intertriginous areas) and report the one whole integer score that describes the average IGA using the following scale:

### 10.2 Clinical Signs of Psoriasis

This evaluation is a static assessment of the overall or "average" degree of severity of each of three key characteristics present within all of the subject's psoriatic lesions in the Treatment Area (defined in Section 5) by the investigator or designee as the subject appears on the day of the evaluation. The investigator should NOT refer to any other evaluations to assist with this assessment. The Visit 1 assessment must be made PRIOR to the first application of the test article or bland emollient and subsequent assessments should be made four hours or more after any application of the test article. At every study visit, the investigator or designee will evaluate all psoriasis plaques in the Treatment Area and report the one whole integer score that describes the average severity for each clinical sign of psoriasis using the following scales:

[figure not shown]
Scaling:

Scarn	16.	
0	Clear	No evidence of scaling.
1	Almost clear	
2	Mild	
3	Moderate	
4	Severe	

Erythema:

0	Clear	
1	Almost clear	
2	Mild	
3	Moderate	
4	Severe	

Plaque Elevation:

#### 10.3 Pruritus

The 5-D Pruritus Scale (7) will be used to assess the subjective and multidimensional experience of the subject's pruritus during the previous two weeks at Baseline and Day 15. Possible scores range from 5 (no pruritus) to 25 (most severe pruritus). The study staff should review the Pruritus Scale (see Appendix 3) with each subject and ask them to indicate the response that best describes their experience. The questionnaire should be completed by the subject at Visit 1, PRIOR to the first test article application and at Visit 3 (Day 15). Pruritus assessed by this evaluation should be reported as an AE only if therapy is required.

[figure not shown]
### 10.4 Percentage Body Surface Area with Active Psoriasis in the Treatment Area

The percent BSA with active psoriasis in the Treatment Area (Section 5) will be calculated and documented at all visits. The investigator may use the assumption that 1% BSA is approximately equal to the surface area of the subject's palm and fingers, with the fingers extended yet grouped together, creating a flat oval-like surface area. For BSA determination, residual discoloration (pigmentation and/or erythema) should not be included. The psoriatic lesions should involve BSA at Baseline (see Section 5.1.1).

### 10.5 Local Skin Reactions (LSRs)

At every study visit, the investigator or designee will evaluate the severity (none, mild, moderate, or severe) of the following LSRs within the areas treated with test article known to be associated with topical application of corticosteroids:

- Telangiectasia
- Skin atrophy
- Burning/stinging
- Folliculitis
- Edema

#### 12. LABORATORY TESTS

### 12.1 Urine Pregnancy Tests (UPTs)

The UPTs will be performed at the study site, if the site is registered and conforms to CLIA regulations for such testing (possesses a current valid CLIA Certificate of Waiver), or at an appropriately registered reference laboratory. The investigator will report the UPT results on the CRFs, in the subject's medical records, and in independent records maintained at the study site. The UPT used must have a minimum sensitivity of 25 mIU of  $\beta$ -HCG/mL.

### 13. END OF STUDY CRITERIA

At the end of each subject's participation in the study, the investigator will complete an End of Study form for all completed and discontinued subjects.

### 13.1 Completion of the Study

Subjects who complete the treatment as specified in the protocol will be considered to have completed the study. This includes the following:

• Any subject who completes 14 (+ 3) days of treatment and completes all of the Visit 3 evaluations.

## 13.2 Subject Discontinuation

A subject may be withdrawn from the study prior to completion for any of the following reasons:

- Whenever the subject decides it is in the subject's best interest to withdraw. NOTE: if the subject decides to withdraw from the study due to an AE then it should be classified as withdrawal due to an AE.
- Whenever the investigator decides it is in the subject's best interest to be withdrawn

- AEs
- Worsening of condition or treatment failure (in the opinion of the investigator)
- Intercurrent illness which may, in the investigator's opinion, significantly affect assessment of clinical status
- Noncompliance
- Pregnancy
- Lost to follow-up
- Sponsor administrative reasons

If a subject withdraws from the study prematurely for any reason, complete the final visit procedures. When a subject is withdrawn from the study for a treatment-related AE (i.e., possibly, probably or definitely related as defined in Section 14), when possible, the subject should be followed until resolution or stabilization of the AE.

Subjects who are prematurely withdrawn or discontinued from the study will not be replaced.

### 13.3 Study Termination

The study may be terminated by the investigator or the Sponsor. If, in the opinion of the investigator, clinical observations made during the study suggest that it may be unwise to continue, he or she may stop the study. A study termination by the investigator will be reported to the Sponsor.

In addition, a written statement fully documenting the reasons for this action will be submitted to the Sponsor by the investigator within five working days.

In the event that the Sponsor chooses to discontinue or terminate the study, appropriate notification will be given to the investigator.

#### 14. ADVERSE EVENT REPORTING

An adverse event (AE) is any untoward medical occurrence associated with the use of a drug in humans, whether or not considered drug related.

An AE (also referred to as an adverse experience) can be any unfavorable and unintended sign (e.g., an abnormal laboratory finding), symptom, or disease temporally associated with the use of a drug, without any judgment about causality. An AE can arise from any use of the drug (e.g., off-label use, use in combination with any drug) and from any route of administration, formulation or dose, including an overdose.

Information on the medical condition of subjects should begin following the subject's written consent to participate in the study and a medical history should be taken at screening. During any wash out and baseline periods, any changes in the health of subjects

should be recorded as changes in medical history unless an event occurred as a result of a study-related procedure and is unanticipated; in such cases, the event should be recorded as an AE and reported to the Institutional Review Board (IRB) as an "unanticipated problem" in accordance with local procedures. Other changes in subject health information becomes AE data when the subject begins dosing with the test article and therefore AE data should be collected from the date of the first dose of test article. These data are considered treatment-emergent AEs.

Timely and complete reporting of all AEs assists TI in identifying any untoward medical occurrence, thereby allowing:

- 1) protection of the safety of study subjects;
- 2) a greater understanding of the overall safety profile of the test article;
- 3) recognition of dose-related test article toxicity;
- 4) appropriate modification of study protocols;
- 5) improvements in study design or procedures; and
- 6) adherence to worldwide regulatory requirements.

Test article is defined as a pharmaceutical form of an active ingredient (or "primary operational component" for devices) or vehicle/placebo being tested or used as a reference in the study, whether blinded or unblinded. AEs may be either spontaneously reported or elicited during questioning and examination of a subject. All AEs must be completely recorded on the AE CRF. If known, the investigator should report the diagnosis of the underlying illness or disorder, rather than its individual symptoms. Subjects experiencing AEs that cause interruption or discontinuation of test article, or those experiencing AEs that are present at the end of their participation in the study should receive follow-up as appropriate. If possible, report the outcome of any AE that caused permanent discontinuation or that was present at the end of the study particularly if the AE is considered by the investigator to be treatment-related (i.e., definitely, probably, or possibly related to test article).

### 14.1 Adverse Event (AE)

All AEs must be recorded on the AE CRF. AEs should be followed to resolution or stabilization (if possible), and reported as serious adverse events (SAEs) if they become serious.

The investigator will instruct the subject to report any AEs that may occur during the study. At each visit, the investigator should ask the subject, in non-directive fashion, about any change in the subject's overall condition since the previous visit.

The severity of each AE, as judged by the investigator, will be recorded on the appropriate AE CRF and will be graded according to the following scale:

Mild - The AE is transient and easily tolerated by the subject.

**Severe -** The AE causes considerable interference with the subject's usual activities, and may be incapacitating or life-threatening.

The investigator must determine the relationship of the AE to the test article according to the following categories:

**Definite** - An event that follows a reasonable temporal sequence from administration of the test article; that follows a known or expected response pattern to the test article; and that is confirmed by improvement on stopping or reducing the dosage, and reappearance of the event on repeated exposure (re-challenge).

**Probable** - An event that follows a reasonable temporal sequence from administration of the test article; that follows a known or expected response pattern to the test article; and that is confirmed by improvement on stopping or reducing the dosage of the test article; and that is unlikely to have been caused by concurrent/underlying illness or other drugs, procedures, or other causes.

**Possible** - An event that follows a reasonable temporal sequence from administration of the test article; that follows a known or expected response pattern to the test article; but may have been caused by concurrent/underlying illness, other drug, procedure, or other causes.

**Unlikely** - An event that does not follow a reasonable temporal sequence from administration of the test article; that does not follow a known or expected response pattern to the test article, or most likely was caused by concurrent/underlying illness, other drug, procedure, or other causes, because of their known effects.

**Not Related** - An event almost certainly caused by concurrent/underlying illness, other drug, procedure, or other causes.

The investigator should categorize the outcome of the AE according to the following categories:

Fatal - Termination of life as a result of an AE.

Not Recovered/Not Resolved - AE has not improved or the subject has not recuperated.

**Recovered/Resolved** - AE has improved or the subject has recuperated.

IND: 107,302 Protocol: 122-0551-310; v2.0

Recovered/Resolved with Sequelae - subject recuperated but retained the pathological conditions resulting from the prior disease or injury.

**Recovering/Resolving** - AE is improving or the subject is recuperating.

Unknown - Not known, not observed, not recorded or subject refused.

An adverse reaction is any AE caused by a drug. Adverse reactions are a subset of all suspected adverse reactions for which there is reason to conclude that the drug caused the event. For the purposes of prescription drug labeling, the term adverse reaction means an undesirable effect, reasonably associated with the use of a drug that may occur as part of its pharmacological action or may be unpredictable in its occurrence.

A suspected adverse reaction is any AE for which there is a reasonable possibility that the drug caused the event.

For the purposes of IND safety reporting, "reasonable possibility" means there is evidence to suggest a causal relationship between the drug and the AE. A suspected adverse reaction implies a lesser degree of certainty about causality than adverse reaction, which means any AE caused by a drug.

An AE or suspected adverse reaction is considered "unexpected" if it is not listed in the investigator brochure or is not listed at the specificity or severity that has been observed; or, if an investigator brochure is not required or available, is not consistent with the risk information described in the general investigational plan or elsewhere in the current application. For example, under this definition, hepatic necrosis would be unexpected (by virtue of greater severity) if the investigator brochure referred only to elevated hepatic enzymes or hepatitis. Similarly, cerebral thromboembolism and cerebral vasculitis would be unexpected (by virtue of greater specificity) if the investigator brochure listed only cerebral vascular accidents. "Unexpected," as used in this definition, also refers to AEs or suspected adverse reactions that are mentioned in the investigator brochure as occurring with a class of drugs or as anticipated from the pharmacological properties of the drug, but are not specifically mentioned as occurring with the particular drug under investigation.

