Study endpoints that are SAEs (e.g., all-cause mortality) must be reported in accordance with the protocol unless there is evidence suggesting a causal relationship between the drug and the event (e.g., death from anaphylaxis). In this case, the investigator must immediately report the event to the Sponsor. In addition, such information should also be provided to the site's respective IRB per their governing guidelines for SAE reporting.

If only limited information is initially available, follow-up reports are required. Should the investigator become aware of a SAE (regardless of its relationship to test article) that occurs within 30 days after stopping the test article, the SAE must be reported in accordance with procedures specified in this protocol. In the event of death, if an autopsy is performed, a copy of the report should be sent to TI, if available.

As required, TI will notify participating investigators of all suspected adverse reactions that are serious and unexpected. This notification will be in the form of an IND safety report of potential serious risks as soon as possible but no later than 15 calendar days after the Sponsor determines that the information is "reportable" according to the criteria listed in 21 CFR Section 312.32. These are:

i) Serious and unexpected suspected adverse reactions,

- ii) Findings from other studies including epidemiological studies, pooled analyses or other clinical studies that suggest a significant risk in humans exposed to the test articles,
- iii) Findings from animal or in vitro tests that suggest a significant risk to humans exposed to the test articles, or reports of significant organ toxicity at or near the expected human exposure, and
- iv) Clinically important increases in the rate of occurrence of serious suspected adverse reactions.

Upon receiving such notices, the investigator must review and retain the notice with the Investigator Brochure and immediately submit a copy of this information to the responsible IRB according to local regulations. The investigator and IRB will determine if the informed consent requires revision. The investigator should also comply with the IRB procedures for reporting any other safety information. Where required, submission of safety updates by the investigator to Health Authorities should be handled according to local regulations.

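### All three related causality categories in Section 14.1 require a known or expected response pattern, so a well-timed adverse event with an unfamiliar pattern cannot be recorded as treatment-related

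*Combined protocol and SAP*

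**What the plan says.** Section 14.1 tells the investigator to place every AE in one of five relationship categories. The definitions of the three related ones share a condition:

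- Definite: reasonable timing, then "known or expected response pattern to the test article; and that is confirmed by improvement on stopping or reducing the dosage, and reappearance" on re-challenge.
- Probable: reasonable timing, the same pattern condition, other causes unlikely, and an event "confirmed by improvement on stopping or reducing the dosage of the test article".
- Possible: reasonable timing and an event "that follows a known or expected response pattern to the test article; but may have been caused by concurrent/underlying illness", or by another drug, procedure or cause.

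Unlikely is the only category that mentions an unfamiliar pattern: an event without reasonable timing, "that does not follow a known or expected response pattern to the test article, or most likely was caused by concurrent/underlying illness" or another such source. Not Related is for events almost certainly due to something else.

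Later in the same section a second standard appears: "A suspected adverse reaction is any AE for which there is a reasonable possibility that the drug caused the event". The section explains that an event or suspected adverse reaction can be unexpected, which it defines by what the investigator brochure lists. Section 14.2 relies on that class when it commits to notifying investigators of "all suspected adverse reactions that are serious and unexpected".

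The introductory text of Section 14 and Section 13.2 both define treatment-related as the Definite, Probable and Possible categories. Section 13.2 attaches a rule to it, for subjects who leave the study because of such an event: "treatment-related AE (i.e., possibly, probably or definitely related as defined in Section 14), when possible, the subject should be followed until resolution". The rule also accepts stabilization as its end point. Section 17.3.2 summarizes all reported AEs by system organ class, preferred term, severity and relationship, by treatment.

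**The concern.** A causality scale should let the investigator record a suspicion about an event not seen before with the product. Here familiarity is a condition of entry to every related category, including the one meant for weak suspicion. An investigator who follows the definitions has no related box for a new reaction, however good the timing and however bare the alternatives.

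The dechallenge condition adds a second gap. Probable requires that the event be "confirmed by improvement on stopping or reducing the dosage of the test article". Treatment runs to Day 15 and Section 9.3 discharges the subject at Visit 3, so improvement after stopping may go unobserved for an event first seen late. If such an event has no rival explanation, Possible is also a poor fit, because it is worded around one.

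At stake is whether the relationship column of the AE summary means what a reader will take it to mean, and whether one event can carry two conflicting causality statements. Safety is part of the primary objective (Section 3).

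**Working it through.** The plan gives no figure on this point, so the check sets the definitions side by side.

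**Step 1. The pattern condition.** In Definite and Probable it is joined to the other conditions by 'and'. In Possible it stands beside timing with no alternative. None of the three says 'or' or 'where applicable'. Count: 3 of 3 related categories require a known or expected pattern; 0 of 3 admit an unfamiliar one.

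**Step 2. Event profiles against the scale.** All three profiles have reasonable timing.

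| Profile | Definite | Probable | Possible | Unlikely | Not Related |
|---|---|---|---|---|---|
| A: unfamiliar pattern, no other cause | no (pattern) | no (pattern) | no (pattern) | depends on reading | no |
| B: unfamiliar pattern, another cause conceivable but not the most likely | no (pattern) | no (pattern) | no (pattern) | depends on reading | no |
| C: known pattern, no other cause, no dechallenge observed | no (dechallenge) | no (dechallenge) | not literally (worded around another cause) | no | no |

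Unlikely has three limbs: poor timing (T), no known pattern (P), another cause most likely (O). Its punctuation does not settle how they combine. For A and B, T is false, P is true and O is false:

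- T or P or O: true
- T and (P or O): false
- (T and P) or O: false

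So a well-timed, unfamiliar event either lands in Unlikely or fits nothing, depending on the reading. For C all three limbs are false, and Unlikely fails on every reading.

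**Step 3. The second standard.** The suspected-adverse-reaction definition in 14.1 contains no pattern condition. Profile A can meet it and still be barred from Possible. No text links or ranks the two standards. For an SAE, Section 14.2 asks for a separate reasonable-possibility assessment, so the same event could be Unlikely on the five-category scale and reasonably possible in the SAE report. A non-serious AE has only the five-category grading.

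**Step 4. Where relatedness is used.**

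| Provision | Depends on relatedness? |
|---|---|
| Relationship breakdown of the AE summary (17.3.2) | yes |
| Follow-up after withdrawal for a treatment-related AE (13.2) | yes |
| Outcome of AEs that stopped treatment or are ongoing at study end (Section 14 introduction) | emphasis only |
| General follow-up of AEs to resolution or stabilization, if possible (14.1) | no |
| Follow-up of AEs that interrupt or stop treatment or are ongoing at the end (Section 14 introduction) | no |
| AE listing and counts by class and term (17.3.2) | no |
| SAE reporting (14.2) | no |
| Safety endpoints (17.2.2) | no |

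**The case against.** The strongest reply is that this is a wording gap in one descriptive classification. Section 14.1 follows all AEs where possible, so the Section 13.2 rule adds little. Section 17.3.2 counts every AE by arm; in a double-blind, vehicle-controlled trial an excess on active foam would show by preferred term without any causality label. All SAEs are reported whatever their relationship. Investigators use judgment, the mention of other causes in Possible can be read as permissive, and the meaning of reasonable possibility is spelled out for IND safety reporting rather than for the AE scale.

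Most of this stands, and it rules out several stronger conclusions that a reader might draw:

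- That such events vanish from the AE tables or from follow-up. The provisions in Step 4 show otherwise, and no related-only table is specified.
- That every unexpected reaction is shut out. In 14.1 that term covers effects known for the drug class but not listed for this drug; these may still follow a known or expected pattern. The firm claim concerns unfamiliar patterns only.
- That the plan is shown to favor a clean safety conclusion. The documents do not say how investigators would resolve the gap, and the by-arm counts are untouched.
- That late telangiectasia or skin atrophy would be missed. Section 10.5 grades both at every visit as known corticosteroid reactions, and Section 17.3.2 tabulates them by arm whatever the cause.
- That counting combinations of conditions measures the problem. It weights hypothetical cases equally and says nothing about how often they occur.

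What does not stand is the appeal to judgment. Section 14.1 makes use of these categories mandatory, and no other text relaxes the pattern condition.

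**Conclusion.** The point holds in a limited form and should be corrected. As written, all 3 related categories exclude a well-timed AE with an unfamiliar pattern, and this is inconsistent with the suspected-adverse-reaction definition in the same section. A known-pattern event with no other cause and no observed dechallenge also has no literal home.

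The effect is misplacement within the relationship breakdown, loss of the specific Section 13.2 trigger and loss of an emphasis in Section 14. It falls mainly on non-serious AEs. The number of events affected cannot be estimated from the documents.

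This rests on a literal reading of the definitions and, for the second gap, on improvement after stopping not being observed. Follow-up after Visit 3 could supply that observation in some cases.

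**What to change.** In Section 14.1 and the CRF completion guidance:

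1. Redefine Possible as a reasonable temporal sequence plus a reasonable possibility that the test article caused the event, whether or not the pattern is known and whether or not another cause exists. Use the section's own meaning of reasonable possibility, which asks for evidence pointing to a causal link. A threshold of merely being unable to exclude causation would be looser and would create a new mismatch.
2. For Probable, make a known pattern and improvement on dechallenge supportive, where applicable, rather than required.
3. State that Possible, Probable and Definite together correspond to a suspected adverse reaction, so that one judgment serves the AE summary, follow-up and IND reporting.
4. As a consequence, word Unlikely so that an unfamiliar pattern alone does not place an event there; otherwise it would overlap with the new Possible.

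The cost is a protocol wording change, with the IRB approval that Section 18.4 requires for amendments, and revised CRF guidance. No endpoint, visit or sample size changes. Somewhat more AEs will be classed as related, in both arms.
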